Outcome measures and covariates. Primary outcome: agitation/aggression score (domain score on the Neuropsychiatric Inventory (NPI), continuous measure from 0-12, longitudinal); Secondary outcome: response (dichotomous, based on 30% decrease in NPI core score (sum of domains for motor activity and agitation/aggression) plus a CGI-C score of much improved or very much improved, longitudinal); Exploratory outcome motor activity score on the NPI. Covariates/Predictor variables: 1) demographic characteristics (e.g., gender, race, age); 2) baseline measures of the corresponding outcomes. Other Measures:1) tolerability, as measured by emergent side effects (TESS scores and adverse events) over the course of the 12 week trial; 2) brain derived neurotrophic factor (BDNF) serum levels.

Sample size and randomization: The randomization will be carried out by the statistician and implemented by the pharmacist, who are both otherwise independent of the research team. The randomization sequences will be balanced in blocks of random size to prevent clinicians from guessing what the next patient's treatment might be.

Modeling longitudinal data and testing hypotheses. Modeling longitudinal data and testing hypotheses. All tests will be two-sided; α =0.05; intent-to-treat with data included for all patients with ≥1 post-baseline assessment. We will use generalized linear mixed models (GLMMs; SAS PROC GLIMMIX) for longitudinal data to evaluate study aims. Models will include fixed effects for treatment group, time, group x time interaction, and any baseline covariates found to be unbalanced despite randomization. Prior to analysis, we will examine all variables at all time points for outliers and inconsistencies and examine their distributions.⁴¹⁻⁴³

Primary hypothesis: *Lithium will significantly reduce agitation/aggression as compared to placebo.*

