The following linear mixed effects model will be used: $Y_{ij} = \beta 0 + \beta 1 I T R T + \beta 2t + \beta 3t^* I T R T + \beta 4X_i + \beta 4X_i$ bi + $\epsilon i j$ where Yij is the agitation/aggression score for the *i*th subject at *t*week, *t* =0, 2,...,12, *yi0* is agitation/aggression at baseline, *liTRT* is the indicator variable for randomized condition (placebo vs. lithium), an indicator of recruitment site (Columbia University Medical Center and Johns Hopkins School of Medicine), and any baseline covariates exhibiting imbalance after randomization, bi is a random intercept to account for repeated measures across time within the patient, and $\epsilon i j$ is a random error term. Significant interaction $t^* liTRT$ indicates that the changes in agitation/aggression in each treatment group is different over time (which corresponds to rejecting the null hypothesis that β 3= 0). The effect of time will be estimated for each group separately and the groups will be compared (using contrast) at the last time point t=12. Secondary hypothesis: Lithium will have greater proportion of responders compared to placebo. We will test whether the probability of response by end of active treatment differs significantly in the lithium and placebo groups by a chi-square test. In addition, we will test whether change in the probability of response differs across treatment groups by longitudinal analysis. We will use the generalized linear mixed effects model: logit(Yij) = $\beta 0 + \beta 1$ liTRT+ $\beta 2t$ + $\beta 3t^{*}$ /*iTRT*+ $\beta 4Xi$ + *bi* + ϵij where Yij is the a binary variable indicating response for the *i*th subject at t week, t = 2, 4, ..., 12. We will first test significance of the treatment effect by testing the group by time interaction.

Exploratory Hypothesis. Lithium will significantly reduce repetitive behaviors as compared to placebo. We will use the same model in the analyses for the primary hypothesis where Yij is the motor activity score for the *i*th subject at *t* week, *t* =0, 2,...,12.

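### The primary model (random intercept only, linear time) gives dependable 95% intervals only under a restrictive condition, and the plan does not say which effect carries the primary interval

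*Combined protocol and SAP*

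**What the plan says.** All references are to the Statistical Procedures and Data Analysis section of the combined protocol and SAP.

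- **Covariance and time.** The primary-hypothesis model has a treatment indicator, one term in t, one t-by-treatment term (β3), a covariate term and an error. In it, "bi is a random intercept to account for repeated measures across time within the patient". No random slope, residual correlation structure, robust standard error or degrees-of-freedom method is given.
- **Baseline.** The model text states that "Yij is the agitation/aggression score for the *i*th subject at *t*week, *t* =0, 2,...,12, *yi0* is agitation/aggression at baseline". The covariate list includes "baseline measures of the corresponding outcomes". Elsewhere baseline covariates enter conditionally: "any baseline covariates found to be unbalanced despite randomization" in the general model description and "any baseline covariates exhibiting imbalance after randomization" in the primary model. The displayed equation shows only a β4Xi term, printed twice, so it is visibly damaged. The absence of a yi0 term there proves nothing.
- **Effect.** A significant interaction is the test of lithium, "which corresponds to rejecting the null hypothesis that" β3 is zero. The text then adds that "the groups will be compared (using contrast) at the last time point t=12".
- **Role of the interval.** The Power Analysis section makes effect sizes with their 95% intervals, not tests, the main results. It does not define the effect size.
- **Reuse.** For the exploratory hypothesis: "We will use the same model in the analyses for the primary hypothesis where Yij is the motor activity score".

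**The concern.** A random intercept with independent errors assumes that weeks 0 and 12 are as strongly correlated as weeks 10 and 12, and that every patient in an arm has the same underlying slope. Repeated behavioural ratings over 12 weeks need not behave like that, and the plan gives no reason to expect it. If correlation decays with time, or slopes vary, the model takes the variance of a slope to be smaller than it is. Both candidate effects, β3 and the week-12 contrast, then get intervals that are too narrow.

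Two further gaps add to this. It is unclear whether baseline is used once or twice. And two effects that can differ numerically are both on offer to carry the primary interval. The interval would inform a larger trial, so false precision would be passed on to its design.

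**Working it through.** **Inputs.** Two-sided α 0.05; 60 randomised, 20% attrition, 48 completers, so 24 per arm if equal; visits at weeks 0, 2, ..., 12, so m = 7, mean time 6, Sxx = 2(36+16+4) = 112. Correlation, slope variance and outcome SD are not stated and are assumed below. Error means how often a nominal 95% interval misses the truth.

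**The plan's own figure.** With 24 per arm and 80% power, a two-sample t-test detects 0.826 SD, which reproduces the upper end of 0.58-0.83. The lower end needs an assumed correlation, and several estimands fit:
- average of 6 visits: 0.826 × √((1+5×0.39)/6) = 0.58;
- week-12 ANCOVA: 0.826 × √(1−0.71²) = 0.58;
- 12-week slope: 0.826 × √(144×(1−0.62)/112) = 0.58.

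So the power range does not show which effect is primary.

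**Covariance, baseline not a covariate.** Let G be the variance of a patient's mean over visits and W the average within-patient variance. The fitted model takes the slope variance as W/112 and the week-12 variance as G + 36W/112. Error = 2[1 − Φ(1.96 × √(model variance/true variance))]; arm size cancels. Under equal correlation both variances are right, and simulated error was 4.6-5.2%.

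*AR(1), 0.8 between adjacent visits, unit variance.* W = 0.4193, G = 0.6406.
- β3: model 0.4193/112 = 0.00374. True 4×35.13/112² = 0.01120, where 35.13 is the sum of x_i x_j 0.8^|i−j| over x = −3, ..., 3. SE ratio 0.578, error 26%.
- Week 12: model 0.6406 + 36×0.00374 = 0.775; true 0.6406 + 36×0.01120 = 1.044. Ratio 0.862, error 9%.
- Simulated over 0.7-0.9: 22.7-29.2% and 7.9-10.0%.

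*Random slopes, intercept and residual variance 0.5 each, SD of 12-week change 0.71 outcome SD.* Slope variance 0.5/144 = 0.00347.
- β3: model (0.5 + 0.00347×112/6)/112 = 0.00504; true 0.5/112 + 0.00347 = 0.00794. Ratio 0.797, error 12%.
- Week 12: G = 0.5 + 0.5/7 + 36×0.00347 = 0.696; model 0.696 + 36×0.00504 = 0.878; true 0.696 + 36×0.00794 + 72×0.00347 = 1.232. Ratio 0.844, error 10%.
- For SDs of 0.35-1.0: 6.6-16.8% and 6.1-13.0%.

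**Baseline as covariate and as week-0 outcome, equal correlation r.** With g = (1+6r)/7, the model's week-12 variance is g − g² + 36(1−r)/112. The true variance adds 72g(1−r)/112, because the baseline row also enters the slope.

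| r | model | true | SE ratio |
|---|---|---|---|
| 0.3 | 0.465 | 0.645 | 0.85 |
| 0.5 | 0.406 | 0.589 | 0.83 |
| 0.7 | 0.287 | 0.431 | 0.82 |

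Simulation with 60 randomised and 12 dropouts gave week-12 error of 9.3, 10.3 and 10.6%; β3 stayed at 4.9-5.5%. With baseline left out, week-12 error was 4.8, 4.5 and 5.1%. With baseline entered only on imbalance (assumed cut-offs p<0.05 to p<0.20) it was 3.8-6.0%. With baseline in but week categorical it was 5.5-6.6% (complete data). The excess therefore needs double use and linear time together.

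**Linear time, true week-12 difference 1.** Fitted week-12 value = mean effect + 6 × slope.
- Plateau at week 6 (0, 1/3, 2/3, 1, 1, 1, 1): 0.714 + 6×9.333/112 = 1.21.
- Start after week 6 (0, 0, 0, 0, 1/3, 2/3, 1): 0.286 + 6×9.333/112 = 0.79.
- Immediate full effect: week 12 gives 0.857 + 6×6/112 = 1.18, while 12×β3 gives 12×6/112 = 0.64.

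**The case against.** The strongest reply is that nothing in the documents shows unequal correlation or varying slopes, and that under equal correlation with baseline left out the model is sound. That stands.

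A reader might infer varying slopes from the 15% and 50% response rates in the Power Analysis section. The documents do not support this. The rates are an example for the responder endpoint, which combines a fall in a two-domain score with CGI-C. They can also arise with one slope per arm. Applying the 30% rule to a single normal score, 15% v 50% needs a difference of 1.036 × √(1.49−1.4r) SD: 0.84, 0.74 and 0.63 at r = 0.6, 0.7 and 0.8. In that setting the random-intercept model without baseline had 5.0-5.1% error for β3 and 5.0-5.5% at week 12. One can assume instead that responders fall linearly by 0.58/0.35 = 1.66 SD and others do not change. Errors are then 10-16% and 9-12%, but that mixture is an assumption, not the plan's. Titration patient by patient does not establish slope variance either.

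It is also fair that double use of baseline is one reading of a damaged equation, that the general model description names time without fixing its form, and that the null hypothesis is tied to β3. The last point settles the test. It does not settle which estimate carries the interval.

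Finally, this is a pilot with a feasibility aim. That limits the consequences, but the same section puts the interval ahead of the test.

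**Conclusion.** The point holds as a cheap improvement, with moderate confidence. The stated model gives valid intervals only under equal correlation and a common slope within arm, and the plan offers no support for that condition. The excess error ranges from nil to the AR(1) and random-slope figures above, depending wholly on assumed values. β3 is the more exposed effect under AR(1). Week 12 is exposed even under equal correlation if baseline is used twice.

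Two other stronger readings should be resisted. The documents do not show that baseline will be used twice. Nor do they show that linear time will exaggerate the effect: it can give about 121% or 79% of the true week-12 difference, and the direction is unknown. What is plainly missing is a statement of how baseline enters and which effect is primary. The feasibility aim and the sample size are unaffected.

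**What to change.** Amend the primary-hypothesis model and the Power Analysis text:

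1. Use baseline once and unconditionally: either response at weeks 2-12 with baseline and baseline-by-week as covariates, or baseline as an outcome only.
2. Make week categorical with group-by-week. Assign every visit to the nearest interval by weeks since randomisation, including early-termination visits and the accelerated or interrupted schedules under Alternate Scenarios. State a rule for ties and for two visits in one interval.
3. Replace the random-intercept-only covariance with an unstructured one and Kenward-Roger degrees of freedom. Pre-state a fallback: random intercept plus slope, or robust standard errors with a small-sample correction.
4. Name the week-12 lithium-minus-placebo difference with its 95% interval as the primary estimate.
5. Apply the same model to motor activity.

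**Cost.** Wording only; no new data. For weeks 2-12 the covariance has 6×7/2 = 21 parameters instead of 2. In simulation, none of 68,000 fits failed and error was 4.8-5.6% in all 17 assumed scenarios. The lighter fallbacks also did well with linear time, baseline left out and slope variation or AR(1) 0.8: coverage was 92.3-96.7% with a random slope and 94.2-95.8% with robust errors (480 runs per scenario). If equal correlation is true, the proposed model, compared with leaving baseline out, loses about 27% in precision at correlation 0.3, loses 8% at 0.5 and gains 17% at 0.7.

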Tolerability: We will assess the tolerability of low dose lithium by assessing emergent side effects over the course of the 12-week trial on lithium compared to placebo. We will compute descriptive statistics of tolerability measures in each treatment group and provide both point estimates and their confidence intervals. We will test whether the change in TESS score from baseline to week 12 differs significantly in the lithium and placebo arms by a t-test.

Biomarker Hypothesis. Increases in BDNF serum levels will be associated with decreases in agitation/aggression and repetitive behaviors. The relationship between change in BDNF serum levels (defined as baseline minus endpoint of active treatment) and the changes in agitation/aggression score and motor activity score (defined as baseline minus treatment endpoint) will be tested using correlation analyses.

Power Analysis. Given the proof-of-concept nature of this study as a pilot, effect sizes with 95% confidence intervals rather than statistical significance testing will be the primary results of interest. The overarching aim is to demonstrate feasibility for conducting a larger trial which would then be used to adequately test efficacy.³³ Nevertheless, we provide some guidance regarding the statistical power available for testing differences between treatments. With n=60 patients randomized (30 to lithium, 30 to placebo) we conservatively examine power below assuming attrition will be 20% (i.e. 48 completers) though our past studies have all had attrition <20% and all available longitudinal data will be used for all individuals regardless of whether they complete the 12 weeks. For the primary outcome of agitation/aggression score measured by the NPI, we will have 80% power to detect a medium to large treatment effect size of 0.58-0.83 with the range depending on the within person correlation over time. Additionally, for responder status, we will have >80% power to detect a difference between, for example, a 15% response rate and a 50% response rate at 12 weeks. Differences among other exploratory outcomes and tolerability measures will be detectable with similar power.

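### The longitudinal responder model is not a valid model for a 0/1 outcome as written, and no estimation method is named; how an analyst resolves this changes the interaction test or the odds ratio

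*Combined protocol and SAP*

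**What the plan says.** All references are to the section Statistical Procedures and Data Analysis of the combined protocol and SAP.

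- Secondary hypothesis: response is tested first by a chi-square test at the end of treatment. A longitudinal model is then added: "We will use the generalized linear mixed effects model: logit(Yij") is set equal to terms for treatment, time, their interaction and covariates, plus bi and εij, "where Yij is the a binary variable indicating response for the" patient at weeks 2 to 12. The test is also named: "We will first test significance of the treatment effect by testing the group by time interaction".
- Primary hypothesis: this is the only place where the two random terms are defined, and the model there is linear. "bi is a random intercept to account for repeated measures across time within the patient", and εij "is a random error term".
- Modeling longitudinal data and testing hypotheses: "We will use generalized linear mixed models (GLMMs; SAS PROC GLIMMIX) for longitudinal data to evaluate study aims". No distribution, estimation method or residual-scale setting follows. "All tests will be two-sided", at α = 0.05.
- Power Analysis: "effect sizes with 95% confidence intervals rather than statistical significance testing will be the primary results of interest".

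**The concern.** The equation takes the logit of the observed 0/1 value rather than of its probability, and it keeps an error term that appears to have been carried over from the linear model for the primary outcome. An analyst must therefore decide what εij means and how to fit the model, and the plan settles neither. With six correlated binary values per patient and at most 30 patients per arm, that choice can matter. One route makes the interaction test too liberal. Another leaves the test sound but pulls the model's odds ratio towards 1. In a pilot that puts estimates and intervals ahead of significance tests, and that is meant to inform a larger trial, the choice should not be left until the data are in hand.

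**Working it through.** **Inputs from the plan.** 60 patients, 1:1; 20% attrition, so 24 per arm; six visits (weeks 2 to 12); two-sided 5%; 15% against 50% responders at week 12.

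**Assumptions.** The SD of the random intercept on the logit scale (1 to 4) and the course of response over time. The documents give neither.

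**The plan's own figure.** The only operating figure for response is power above 80% for 15% against 50%. It concerns two proportions, not the longitudinal model. With 24 per arm and mean proportion 0.325:

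- null SE = √(2 × 0.325 × 0.675 / 24) = 0.1352
- alternative SE = √((0.1275 + 0.25) / 24) = 0.1254
- power = Φ((0.35 − 1.96 × 0.1352) / 0.1254) = Φ(0.68) = 75.1%

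With 30 per arm it is 84.3%. The figure is therefore not reproduced at 48 completers, but that is a separate matter. The plan states no type I error or odds ratio for the longitudinal model, so there is nothing further to reproduce.

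**Step 1: the formula.** logit(p) = log(p / (1 − p)), which is −∞ at 0 and +∞ at 1. A binary variable has variance p(1 − p), fixed once p is known, so there is no residual variance left to estimate.

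**Step 2: type I error of the interaction test.** Three fits were compared on simulated random-intercept logistic data: (a) pseudo-likelihood with εij treated as a free residual scale φ; (b) pseudo-likelihood with no εij and scale 1; (c) maximum likelihood by quadrature with no εij. The fits were hand-coded; PROC GLIMMIX itself was not run.

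- S1: SD 1, 2, 3; response 5% rising to 25% in both arms; 400 sets per scenario.
- S2: separate code; 60 patients, 20% dropout; SD 1 to 4; week-12 response 16 to 50%; 1,000 sets per scenario (500 for the 16% case, fits (a) and (b) only).
- S3: 24 per arm; SD 1, 2, 3; 250 sets.

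| Rejection of a true null, nominal 5% | (a) free scale | (b) scale 1 | (c) quadrature |
|---|---|---|---|
| S1, 24 per arm | 13.5, 18.5, 28.1% | 2–5% | 2–5% |
| S1, 30 per arm | 13.0, 20.6, 25.4% | 2–5% | 2–5% |
| S2 | 8.7–30.0% | 2.1–4.5% | 4.0–5.3%; 6.3% with an unmodelled random slope |
| S3 | 14, 24, 34% | 3–4% | 4–5% |

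Monte Carlo SE: √(0.34 × 0.66 / 250) = 3.0 points for the 34% entry, and √(0.05 × 0.95 / 1000) = 0.7 points for a 5% entry in S2.

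The cause is that φ is estimated well below 1: medians 0.65, 0.44, 0.33 in S1 and 0.38 to 0.71 in S2. If standard errors scale roughly with √φ, the true size is about 2Φ(−1.96√φ). For the S1 medians that gives 11.4%, 19.4% and 26.0%, close to the simulated 13.5%, 18.5% and 28.1%.

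**Step 3: conditional log odds ratio at week 12 under fit (b).**

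| Scenario | True | Mean or median, (b) | Shrinkage |
|---|---|---|---|
| S1, SD 1 | 2.05 | 1.86 | 9% |
| S1, SD 2 | 2.75 | 2.18 | 21% |
| S1, SD 3 | 3.61 | 2.41 | 33% |
| S2, SD 2 | 2.0 | 1.57 | 21% (OR 4.8 against 7.4) |
| S2, SD 3 | 2.5 | 1.72 | 31% (OR 5.6 against 12.2) |

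S1 is 15% against 50% at week 12 with 24 per arm (500 sets, means); S2 gives medians. Coverage of the 95% interval for SD 1, 2, 3 was 93, 88, 70% in S1 and 93, 85, 64% in S3. Quadrature gave 95% throughout in S1 and 94, 97, 96% in S3.

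**Step 4: power of the planned interaction test, (c) against (b).** S3: 39 v 34%, 42 v 34%, 46 v 38%, a gain of 5, 8 and 8 points. S2: 37.5 v 29.4% and 39.9 v 29.6%, a gain of 8.1 and 10.3 points.

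**Step 5: week-12 difference in response probability, averaged over bi.** True value 0.35, 400 sets per SD. Fit (b) averaged 0.335, 0.324, 0.326, so it is low by 1.5, 2.6 and 2.4 points. Fit (c) averaged 0.350, 0.346, 0.346.

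**The case against.** The strongest reply is that εij is loose notation. The plan speaks of generalized linear mixed models, a binary variable and a probability of response, so the natural reading is an ordinary logistic model with a random intercept, and then the test is not inflated. Nor does the literal equation imply a residual scale, since εij is added inside the linear predictor. When εij was fitted that way by pseudo-likelihood (24 per arm, 250 sets), the interaction test rejected 2.4% and 4.0% at SD 1 and 2, the same as fit (b). The estimated variance of εij fell below 0.01 in 97% and 100% of sets. SD 3 was not completed. This stands: the inflation belongs to one, less natural, implementation.

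It is also fair that the plan never asks for an odds ratio. It gives response as proportions, and on that scale the bias is small and the root mean squared error of pseudo-likelihood is no worse (0.096, 0.107, 0.107 against 0.097, 0.111, 0.113 for quadrature). Quadrature is not flawless either. Its mean log odds ratios in S1 were 2.08, 2.92 and 3.82 against 2.05, 2.75 and 3.61, about 1, 6 and 6% high, and its root mean squared error on that scale was larger at SD 1 and 2 (0.69 v 0.64; 1.10 v 1.00).

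What survives is that the equation is wrong as printed, that the plan fixes no estimation method, and that even under the ordinary reading the method affects power and the coverage of the conditional odds ratio.

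**Conclusion.** The model needs correcting, but the consequence is limited and conditional. With εij as a free residual scale, the interaction test is anti-conservative, at roughly 9 to 34%. With εij dropped and pseudo-likelihood at scale 1, the test holds its level (about 2 to 5%) but gives up about 5 to 10 points of power. The conditional log odds ratio then shrinks by about 9 to 33%, with clear under-coverage at the larger SDs. The probability difference moves by only about 2 to 3 points.

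A reader might infer that the planned responder analysis has both an inflated error rate and a shrunken odds ratio. The documents do not support that. The two faults come mainly from different fits: in S2 the free-scale fit shrank the log odds ratio less (1.83 against 2.0; 2.21 against 2.5). No single error rate can be attached to the plan, because the SD and response course are assumed. The documents also do not say which method the software would apply unprompted, and the point does not depend on it. The chi-square test named first for this hypothesis is unaffected, as is the primary outcome.

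**What to change.** Under Secondary hypothesis, replace the equation with

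logit P(Yij = 1 | bi) = β0 + β1·TRT + β2·t + β3·t·TRT + β4·Xi + bi,

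with no εij. State a binary distribution with logit link, fitted by maximum likelihood with adaptive quadrature and no residual-scale term. Report the week-12 difference in response probability, averaged over bi, with its 95% interval. That puts the model on the same scale as the chi-square comparison and the 15% against 50% in the Power Analysis.

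The cost is one formula and one software option. The downside is a longer run time and occasional non-convergence when few patients respond.

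### In the responder mixed model, the group-by-time interaction is named as the test of the treatment effect although every modelled visit is post-baseline; a week-12 contrast should be named instead

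*Combined protocol and SAP*

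**What the plan says.** All references are to the section Statistical Procedures and Data Analysis unless stated otherwise.

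- The secondary hypothesis concerns the level of response: "Lithium will have greater proportion of responders compared to placebo".
- Two analyses follow. The first asks whether "the probability of response by end of active treatment differs significantly in the lithium and placebo groups by a chi-square test". The second is a supplement: "In addition, we will test whether change in the probability of response differs across treatment groups by longitudinal analysis".
- The second analysis is a random-intercept logistic model with group, linear week and their product. Its time points are weeks 2, 4, ..., 12, with no week 0.
- For that model the plan then states: "We will first test significance of the treatment effect by testing the group by time interaction". No second step, main-effect test or week-12 contrast is written for response.
- For the primary outcome the time points start at week 0, and a between-group contrast at week 12 is written in addition to the interaction.
- On error rates: "All tests will be two-sided; α =0.05". The Power Analysis paragraph claims, for responder status, ">80% power to detect a difference between, for example, a 15% response rate and a 50% response rate at 12 weeks", under 20% attrition from 60 randomized patients (48 completers).

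**The concern.** The interaction is a reasonable test of treatment in the primary model. Randomized groups should be alike at week 0, so an effect must show as diverging change. Response is defined relative to baseline and does not exist at week 0, so the responder model starts after two weeks of treatment. There the interaction asks whether the group difference in log-odds changes between week 2 and week 12. It does not ask whether there is a difference.

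The secondary hypothesis is about a difference. If lithium patients respond early and stay responders, the named test of the treatment effect will tend to be null, while the chi-square on the same patients may be significant. The plan does not say how to read such a pair. The model's estimate is also affected: beta3 with its confidence interval does not estimate the hypothesized effect.

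**Working it through.** **Inputs from the documents.** Two-sided alpha 0.05; 60 patients, 30 per arm; 20% attrition, so 24 completers per arm; 15% v 50% at week 12; visits at weeks 2, 4, ..., 12.

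**Assumptions, because the documents give no values.** Random-intercept SD of 1.5 or 2.5 on the logit scale, and the response rates before week 12. Eight trajectories were tried, all ending at 15% v 50%.

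**Step 1: the plan's own figure.** Pooled chi-square power is Phi[(d - 1.96*SE0)/SE1], with d = 0.50 - 0.15 = 0.35 and mean rate 0.325.

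- 24 per arm: SE0 = sqrt(2*0.325*0.675/24) = 0.1352; SE1 = sqrt((0.15*0.85 + 0.50*0.50)/24) = 0.1254; (0.35 - 0.2650)/0.1254 = 0.68; power 75.1% (exact enumeration 76.7%).
- 30 per arm: SE0 = 0.1209; SE1 = 0.1122; (0.35 - 0.2370)/0.1122 = 1.01; power 84.3% (exact 84.7%).

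The stated power above 80% is met with all 60 patients but not with 48 completers. An unpooled variance gives 79.7% at 24 per arm, so this is a question of which base was used rather than a clear error. For the present point, the chi-square has about 75-77% power in completers.

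**Step 2: what the interaction measures.** In the responder model the lithium-placebo log-odds difference at week t is D(t) = beta1 + beta3*t. Hence D(12) - D(2) = 10*beta3. If D(2) = D(12), then beta3 = 0 and the whole difference is beta1. The test of beta3 = 0 then rejects at about alpha, whatever the size of beta1. This step is algebra and needs none of the assumptions.

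**Step 3: simulation.** The plan's model was fitted by maximum likelihood (25-point Gauss-Hermite quadrature) to 60 patients with 12 random dropouts. There were 1000 trials per case, so the Monte Carlo standard error is at most 1.6 points. The interaction was tested by likelihood ratio and the week-12 contrast beta1 + 12*beta3 by a Wald test. Each cell gives SD 1.5 / SD 2.5.

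| Trajectory (placebo v lithium), ending at 15% v 50% | Interaction | Week-12 contrast |
|---|---|---|
| A. Constant from week 2 | 4.8% / 5.8% | 92.2% / 89.4% |
| B. Both arms rise, constant odds ratio | 5.4% / 6.0% | 90.1% / 84.6% |
| C. 10% v 20% at week 2, full difference from week 4 | 13.9% / 17.7% | 96.7% / 94.6% |
| D. Plateau from week 6 | 26.8% / 31.6% | 97.5% / 96.4% |
| E. Plateau from week 8 | 44.9% / 49.3% | 97.3% / 95.4% |
| F. Steady divergence from 5% v 5% | 45.4% / 53.2% | 86.5% / 83.6% |
| G. Steady divergence from 10% v 10% | 59.9% / 67.8% | 90.6% / 87.2% |
| H. Placebo flat at 15%, lithium rising from 15% | 66.4% / 77.3% | 92.4% / 88.7% |

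On the same data the week-12 chi-square in completers rejects in 76.5% of trials, and a chi-square on the last available observation in 74% to 85%.

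**Step 4: cross-check.** A second simulation (400 trials per case, SD 1.5) gave interaction v contrast power of 6% v 91% (constant), 26% v 98% (plateau from week 6), and 38% v 91% and 63% v 94% (two forms of steady divergence). The lower of these, 38%, is why the range for a growing effect is given as roughly 40-77%. Type I error of the contrast was 5.5%.

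In rows C to E a straight line in time is fitted to a curve. The contrast's high power there shows that it detects the difference, not that its week-12 estimate is unbiased.

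**The case against.** The strongest reply is that the plan already tests the level of response by the chi-square, and that the model is introduced for a different question, change over time, for which the interaction is the matching test. This largely stands. What it does not explain is the sentence that calls the interaction the test of the treatment effect, or the lack of a week-12 contrast such as the one written for the primary outcome.

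Three stronger readings are tempting, and the documents do not support them.

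- *A lasting difference would usually be declared non-significant.* Not by the secondary analysis as a whole. The chi-square is listed first, does not depend on the interaction, and would find 15% v 50% in about three trials out of four.
- *A null interaction means that no treatment effect is reported.* No such rule is written. The word "first" implies a later step that is missing, which is incomplete wording rather than a decision rule, and nothing lets the interaction override the chi-square.
- *The model has almost no power.* That holds for a constant difference. The Introduction describes dose steps at weeks 2, 4 and 6, so an effect that keeps growing to week 12 is plausible, and power is then roughly 40-77%. An early or plateaued response is plausible too, since dose increases are tied to absence of response at lower doses.

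It is also fair that this is a secondary outcome in a pilot whose Power Analysis paragraph puts effect sizes and intervals ahead of significance tests. That limits the harm, but it also favours an estimate of the week-12 difference over one of beta3.

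**Conclusion.** The point holds for the longitudinal responder analysis only. The sentence assigns the treatment effect to a coefficient that is zero whenever the difference is established by week 2 and held; rejection is then about 5%. If the difference plateaus by weeks 4 to 6, power is about 14-32%; by week 8, 45-49%; if it grows to week 12, roughly 40-77%. The week-12 contrast of the same model gives 84-98% in every case tried, so its lowest value exceeds the interaction's highest.

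The 5% result is algebraic. The other figures rest on assumed trajectories and random-intercept SDs, on 15% v 50% at week 12, and on dropout at random. The hypothesis itself remains tested by the chi-square. The practical consequence is that the two analyses can disagree with no stated way to resolve it, and that the model as specified gives no estimate of the hypothesized effect. This merits a correction of wording; it does not undermine the secondary outcome.

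**What to change.** Replace the sentence with:

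> In the longitudinal model the treatment effect on response is the lithium-placebo log-odds difference at week 12 (beta1 + 12*beta3), reported with its 95% CI. The group-by-time interaction is reported separately as the test of whether the difference changes over time.

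Add one line saying that the chi-square is the main test of the secondary hypothesis and that the model contrast is supportive.

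The cost is two or three sentences of SAP text, with the same model and data, and the stated question about change is kept. There is a small downside. The contrast relies on linear time on the logit scale, and it is a second test of the same week-12 question, so its supportive status should be fixed before unblinded data are analysed.
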